4.2.2 Safety in Hemodialysis Patients

A review of the aggregate safety data shows that CR845 was well tolerated in hemodialysis patients when administered after each dialysis session for up to 8 weeks at IV doses ranging from 0.5 mcg/kg to 6 mcg/kg. Although patients exposed to CR845 reported more adverse events compared with placebo patients, most events were mild or moderate in nature. Generally mild, transient paresthesias (facial tingling) and/or hypoesthesias (in different anatomic locations), mostly on the first week of dosing, as well as headache, dizziness, and somnolence, were the most frequently reported adverse events associated with CR845 administration. Of note, side effects (eg, dysphoria and hallucinations) commonly associated with centrally-acting kappa opioids were not reported in patients exposed to CR845. Consistent with its lack of affinity for mu-opioid receptors, CR845 did not cause euphoria, respiratory depression, or reduction in oxygen saturation.

CR845-CLIN2101 (Part A) evaluated the safety, pharmacokinetics, and efficacy of repeated IV doses of CR845 compared to placebo over an 8-week treatment period in 174 hemodialysis patients. This study is the longest treatment period evaluated to date in hemodialysis patients and no clinically important or significant safety findings related to CR845 were noted. As expected with patients on hemodialysis, a significant number of the reported serious adverse events (SAEs) were considered not treatment-related, but related to the disease and/or comorbid conditions. There were 31 (17.8%) of 174 patients randomized and treated in the study who had treatment-emergent SAEs. Of the 31 SAE reports, 4 (9%) occurred in 45 placebo-treated patients and 27 (21%) in 129 CR845-treated patients. Only 1 SAE of mental status changes (moderate in severity) in a patient who received CR845 1.5 mcg/kg IV was considered by the Investigator to be probably related to study drug. However, based on the Sponsor's medical review, an alternate etiology of urgent/emergent hypertension offers a more plausible explanation for the acute change in mental status. There were 4 patient deaths (2.3%) in the study, all of which were considered not related to the study drug.

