CR845-CLIN2101 (Part A) evaluated the safety, pharmacokinetics, and efficacy of repeated IV doses of CR845 compared to placebo over an 8-week treatment period in 174 hemodialysis patients experiencing moderate-to-severe uremic pruritus daily or near-daily for 4.4 years on average. The study was conducted at 33 dialysis centers and assessed the effect of 3 doses of CR845 (ie, 0.5 mcg/kg, n=44; 1 mcg/kg, n=41 and 1.5 mcg/kg, n=44) or placebo (n=45) administered at the end of each dialysis session (ie, 3 times/week). The primary efficacy endpoint for Study CR845-CLIN2101 (Part A) was based on itch intensity measurement and defined as the change from a 1-week baseline recorded prior to the start of study drug to the last week of the 8-week treatment period with respect to the weekly mean of the daily 24-hour Worst Itching Intensity numerical rating scale (NRS) score. The least squares (LS) mean (\pm standard error [SE]) treatment group difference from placebo at Week 8 across all CR845 doses was -1.3 (\pm 0.41) (95% confidence interval [CI]: -2.1 to -0.5) ($p=0.002$) with an average NRS score reduction from baseline of -3.2 (\pm 0.22) (LS mean \pm SE) and 95% CI ranging from -3.7 to -2.8. Examination of the individual CR845 dose group results for the Full Analysis Population indicates that a substantial improvement over placebo was observed with all 3 doses. These differences from placebo were statistically significant for the lower dose group of 0.5 mcg/kg ($p<0.001$) and the 1.5 mcg/kg group ($p=0.019$), with an effect size estimated as 0.82, 0.39, and 0.62 for the 0.5, 1.0, and 1.5 mcg/kg doses, respectively. Average reduction from baseline (LS mean \pm SE) ranged from -2.8 (\pm 0.38) in the 1.0 mcg/kg dose group (95% CI ranging from -3.5 to -2.0) to -3.8 (\pm 0.38) in the 0.5 mcg/kg dose group (95% CI ranging from -4.5 to -3.1).

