8.8 Safety Analysis

Analysis of all safety data collected during the Double-blind Phase will be performed on the Double-blind Safety Population. The SAP will provide further detail for the analyses to be applied to each safety parameter, and will also include analyses of safety data collected during the Open-label Phase and during exposure to CR845 during both the Double-blind and Open-label Phases. No statistical hypothesis testing will be carried out and no inferential statistical analysis of the safety parameters will be performed.

The baseline value for all analyses of double-blind safety parameters will be defined as the last value obtained prior to the first dose of double-blind study drug and will include both scheduled and repeat (unscheduled) observations.

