2.1.2 Secondary Objectives

The secondary objectives are:

- To evaluate the efficacy of IV CR845 at a dose of 0.5 mcg/kg compared to placebo in improving itch-related quality-of-life measures in hemodialysis subjects with moderate-to-severe pruritus.
- To evaluate the safety of IV CR845 at a dose of 0.5 mcg/kg in hemodialysis subjects with moderate-to-severe pruritus.

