- TEAEs leading to study discontinuation by SOC and preferred term
- TEAEs potentially related to withdrawal by preferred term – see definition below (for Double-blind Discontinuation Population and Double-blind Discontinuation Safety Population)

Adverse events potentially related to withdrawal that occur during the 2-week Discontinuation Period will be identified based on a blinded review of the data using published criteria [[American Psychiatric Association 2013](#)]. First, subjects that have 3 or more AEs occurring within 6 days (which will include 3 dialysis visits) of the last dose of double-blind study drug from the list below programmatically will be selected for review:

1. Dysphoric mood
2. Nausea and/or vomiting
3. Muscle aches
4. Lacrimation and/or rhinorrhea
5. Pupillary dilation, piloerection, and/or sweating
6. Diarrhea
7. Yawning
8. Fever
9. Insomnia

The data for patients that have AEs potentially related to withdrawal (based on the above criteria) will be reviewed in a blinded fashion. Cases categorized as possibly related to withdrawal will be flagged and separate summaries will be produced for the Discontinuation Period and the Discontinuation Period Safety populations.

In addition, all adverse events will be listed in chronological order including subject identifier, age, race, gender, and all related event status information (start and stop dates, whether the event was ongoing, study day of onset, severity, seriousness, relationship to study drug, action taken with study treatment, and outcome). Note: For the all adverse event listing only, any screen failure subject who has an adverse event after signing ICF

will be included for completeness. Separate listings will be generated for serious adverse events (SAEs), deaths, and adverse events leading to treatment discontinuation. Additionally, a coding list of preferred terms and the verbatim text associated with them will be produced.

The incidence of TEAEs in each CMQ category (see Section [16.2](#)) will be summarized. If a subject experienced more than 1 episode of an adverse event, the subject is counted once for that preferred term; the total number of subjects reporting an event in the category will also be reported.

No statistical tests will be performed on adverse events.

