10.2 Incidence of Infections Related to Uremic Pruritus

Incidence of infections related to uremic pruritus occurring during the Double-blind Treatment Period based on adverse events, hospitalizations, and/or use of antibiotics for treatment of infection related to uremic pruritus will be reported with counts and percentages for each treatment group. These will be compared using Fisher's Exact Test.

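### Adverse events, serious TEAEs, deaths and AESIs are reported by arm with no between-arm estimate or interval, so the planned report does not state what excess the trial rules out.

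*SAP*

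**What the plan says.** Safety is a stated secondary objective in both documents. SAP 2.1.2 words it as "To evaluate the safety of IV CR845 at a dose of 0.5 mcg/kg in hemodialysis subjects with moderate-to-severe pruritus".

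SAP 9.2 lists the adverse event output:
- The number and percentage of subjects by arm, for TEAEs, serious TEAEs, TEAEs leading to study drug discontinuation and AESIs, among others.
- Events per 1000 person-years, for AESIs, serious TEAEs and TEAEs leading to death.

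The section closes with "No statistical tests will be performed on adverse events". Protocol 8.8 is broader: "no inferential statistical analysis of the safety parameters will be performed". The Protocol Synopsis likewise limits safety to descriptive summaries. None of these places names a between-arm difference, ratio or interval.

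Other outcomes are treated differently:
- **Infections related to uremic pruritus**, identified partly from adverse events: "These will be compared using" Fisher's exact test (SAP 10.2; also Protocol 8.9.2).
- **ShOWS and OOWS**: compared between arms by ANCOVA (SAP 10.5).
- **PGIC**, outside the testing sequence: a common odds ratio with exact 95% CI and Clopper-Pearson intervals for each proportion (SAP 8.2.5.3).

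On Phase 2, Protocol 4.2.2 reports: "Of the 31 SAE reports, 4 (9%) occurred in 45 placebo-treated patients and 27 (21%) in 129 CR845-treated patients".

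**The concern.** The sponsor's own background contains a difference in serious adverse events that a 174-patient study could neither confirm nor dismiss. The present trial is larger, is randomized 1:1 and uses one dose, so it is the natural place to narrow that uncertainty.

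Percentages by arm with no interval leave two misreadings open. A chance difference can be taken as harm, and a real one can be dismissed as noise. If the arms come out similar, the report will not say how large an excess has been excluded. That is the figure a safety objective most needs.

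The person-year rates have a further gap. Their numerator counts events, so one subject can contribute several. A reader cannot build a valid interval for such a rate from the printed totals.

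**Working it through.** **1. The plan's own figures.** Protocol 4.2.2 gives the Phase 2 counts: 4/45 = 8.9%, 27/129 = 20.9%, and 31/174 = 17.8% overall. These match the printed 9%, 21% and 17.8%. The documents give no precision or detectable excess for safety. The sample size is set on efficacy alone (Protocol 8.2, SAP 2.6).

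**2. Phase 2 difference.** 20.9% - 8.9% = 12.0 points. The Newcombe interval combines the two Wilson intervals:
- CR845, 27/129: 14.8% to 28.7%.
- Placebo, 4/45: 3.5% to 20.7%.
- Lower limit: 12.04 - √[(20.93 - 14.80)² + (20.73 - 8.89)²] = 12.04 - 13.34 = -1.3.
- Upper limit: 12.04 + √[(28.74 - 20.93)² + (8.89 - 3.51)²] = 12.04 + 9.48 = 21.5.

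Fisher's exact p is 0.075, and the risk ratio is 2.35 (95% CI 0.87 to 6.36). The Wald interval is 1.2 to 22.9. Wald excludes zero and Newcombe does not, which is a reason to name the method in advance.

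**3. What those counts are.** Protocol 4.2.3 gives the doses behind the 129: 0.5 mcg/kg (n=44), 1.0 mcg/kg (n=41) and 1.5 mcg/kg (n=44), over 8 weeks. SAEs by dose are not given, so the figure for the dose studied here is unknown.

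**4. Precision available in this trial.** Assume that all randomized patients are dosed, so 175 per arm (250 if increased), and that SAE proportions lie between about 9% and 25%. The documents do not give the upper end of that range. The half-width is 1.96 × √[p₁(1-p₁)/n + p₂(1-p₂)/n].

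| Proportions, CR845 / placebo | 175 per arm | 250 per arm |
|---|---|---|
| 8.9% / 8.9% | 6.0 points | 5.0 points |
| 17.8% / 17.8% | 8.0 | 6.7 |
| 20.9% / 20.9% | 8.5 | 7.1 |
| 25% / 20% | 8.7 | 7.3 |

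For the last row: 1.96 × √[(0.1875 + 0.1600)/175] = 0.087, and 1.96 × √[(0.1875 + 0.1600)/250] = 0.073.

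**5. Two scenarios, Newcombe limits.**
- *Equal observed proportions.* At 175 per arm the upper limit is +6.2 points near 9%, +8.0 near 17.8% and +8.6 near 21%. At 250 per arm it is +5.1, +6.7 and +7.1. Each is below 12.
- *The Phase 2 split recurs.* 37/175 against 16/175 gives 4.5 to 19.5 points. 52/250 against 22/250 gives 5.8 to 18.2.

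Either result would be informative, and the planned tables would print neither interval.

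**The case against.** Descriptive safety reporting is a deliberate choice, stated in both documents. No safety hypothesis or margin is set. Patient protection does not rest on these tables, because a DSMB reviews safety throughout and its analyses are outside the SAP. These points stand and limit the weight of the concern.

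Four stronger readings are tempting, and the documents do not support them.

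- *The trial cannot say what excess it rules out.* Counts and denominators by arm will be reported, so a reader can work out the risk-difference interval for serious TEAEs. The gap is in what the report states. It is harder to fill for the person-year rates, because of repeat events.
- *Safety has no between-arm inference at all.* Infections are tested and the withdrawal scales are modelled.
- *The SAP forbids intervals.* Its sentence bars tests. The absence of intervals follows from the list of tables and from the wider wording in the Protocol.
- *Phase 2 showed an excess.* The interval includes zero, three doses are pooled, and Protocol 4.2.2 says that many of the SAEs were considered unrelated to treatment.

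The apparent inconsistency is also narrow. ShOWS and OOWS are scale scores, so ANCOVA on them breaks no rule about adverse events. Only the infection test, partly derived from adverse events, sits awkwardly with Protocol 8.8.

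**Conclusion.** The point holds for adverse events, serious TEAEs, deaths and AESIs: no between-arm estimate or interval is planned, and the planned report will not state the excess ruled out. It is a reporting gap that is cheap to close. It biases no estimate and does not touch the primary analysis.

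The Phase 2 imbalance of 12.0 points (95% CI -1.3 to 21.5) is unresolved and is not a demonstrated harm. On the assumptions above, an interval in this trial would extend about 6 to 9 points either side of the difference at 175 per arm, and 5 to 7 at 250. Equal observed proportions within the Phase 2 range would therefore exclude a 12-point excess. That range may not carry over from 8 weeks of pooled doses to 12 weeks at 0.5 mcg/kg. Higher proportions would widen the interval and lower ones would narrow it.

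**What to change.** Add to SAP 9.2:

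> For serious TEAEs, TEAEs leading to death, TEAEs leading to study drug discontinuation and each AESI category in the Double-blind Treatment Period, the CR845-minus-placebo difference in the proportion of subjects will be presented with a 95% CI (Newcombe method). For the rates per 1000 person-years, the between-arm rate ratio will be presented with a 95% CI that allows for repeat events within a subject. These intervals are descriptive. No p-values will be given and no multiplicity adjustment will be made.

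A score interval would serve as well as Newcombe, but one method should be named. For the rates, the SAP should also name the variance method, for example Poisson regression with robust standard errors, and say what is shown when an arm has no events.

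Record the change in SAP Section 12. The SAP has primacy over the Protocol (SAP Section 1, Protocol 8.1), so no amendment is needed. The same entry can note that the infection test is an intended exception to Protocol 8.8.

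The cost is a short SAP paragraph and a few table columns, with no change in sample size or alpha. The downside is chance findings. There are 11 AESI categories and three other outcomes, so 14 risk-difference intervals. If no true difference existed, about 14 × 0.05 = 0.7 would be expected to exclude zero. The descriptive label is there for that reason.

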9.3 Deaths, Serious Adverse Events, and Other Significant Adverse Events

An SAE is defined as any adverse event occurring at any dose and regardless of causality that results in death, is life-threatening, requires in-patient hospitalization or prolongation of existing hospitalization, results in persistent or significant disability/incapacity, is a congenital anomaly/birth defect, or is an important medical event.

Serious adverse events will be collected on the electronic CRF (eCRF) from the date the ICF is signed up to the Follow-up Visit or 7 days following the last dose of study drug, whichever is later. Serious adverse events that occur after the Follow-Up Visit and up to 30 days thereafter should also be documented on an SAE form if they are deemed by the investigator to be “related” to the study drug. Serious adverse events that occur after the Follow-up Visit and up to 30 days thereafter do not need to be documented on an SAE form if they are deemed by the investigator to be not related to study drug. A more detailed definition of SAEs is provided in Protocol Section 6.5.4. The analysis of SAEs is similar to that of adverse events described in Section [9.2](#).

Subject deaths are captured on the *Adverse Events* eCRF page. Subject death listings will include all death data available, including date of death and cause of death. Additionally, SAEs and adverse events resulting in discontinuation will be listed as discussed in Section [9.2](#).

9.4 Clinical Laboratory Evaluation

Summaries of actual values and the changes from baseline to each time point (when applicable) will be presented for quantitative laboratory parameters (e.g., white blood cell count, lymphocyte count). Only data from the central laboratory will be used.

Baseline is defined as the last measurement taken on or prior to the first day of dosing. Note that the Day 1 assessment can be included in the evaluation of baseline if the assessment is performed prior to dosing.

All laboratory evaluation summaries will include the subjects in the Double-blind Safety Population who have at least 1 post-baseline time point (for criteria based on

post-baseline assessments) and with both a baseline and at least 1 post-baseline time point (for criteria evaluating changes from baseline).

Laboratory values will be reported in Système International units.

Laboratory test results will be classified according to whether the value was below (L), within (N), or above (H) the laboratory parameter reference range. A summary of treatment-emergent shifts will compare the baseline L/N/H classification for each laboratory test to the highest and/or lowest L/N/H classification during the treatment period. Clinically important laboratory values based on pre-specified criteria appropriate for the study population will also be summarized.

Additionally, alanine aminotransferase, aspartate aminotransferase, bilirubin, and alkaline phosphatase will be presented in a separate table, with 3× and 5× upper limit of normal (ULN) flagged for alanine aminotransferase and aspartate aminotransferase; 2×ULN flagged for bilirubin, and 1.5×ULN flagged for alkaline phosphatase.

9.5 Vital Signs, and ECG

9.5.1 Vital Signs

Summary tables for vital signs will include descriptive statistics (number of subjects, mean, standard deviation, median, minimum, and maximum) for baseline and each post-baseline assessment. Descriptive statistics will be calculated on both the actual values and the change from baseline. Baseline is defined as the last measurement taken on or prior to the first day of dosing. Note that the Day 1 assessment can be included in the evaluation of baseline given that the assessment is performed prior to dosing.

All double-blind vital sign summaries will include the subjects in the Double-blind Safety Population or Double-blind Discontinuation Safety Population who have at least 1 post-baseline assessment (for criteria based on post-baseline assessments) and with both a baseline and at least 1 post-baseline assessment (for criteria evaluating changes from baseline).

Clinically notable vital signs will be identified based on the criteria below. For each vital sign parameter, the number and percentage of subjects with at least 1 notable value will be tabulated by week and overall for the Double-blind Treatment Period and Discontinuation Period separately.

Vital Sign Parameter	Value
Systolic blood pressure	≥180 mm Hg
	≤90 mm Hg
Diastolic blood pressure	≥100 mm Hg
	≤60 mm Hg
Heart rate	>130 bpm
	<55 bpm

bpm = beats per minute

All vital signs will be listed in by-subject listings, including visit and collection date/time, and will be sorted by subject identifier and date/time of assessment.

9.5.2 12-Lead ECGs

Standard 12-lead ECG readings with the subject in a supine position will be performed. Electrocardiogram results include an overall interpretation of “normal,” “abnormal but not clinically significant,” or “abnormal and clinically significant.” These results will be tabulated by treatment group and overall at each time point. Electrocardiogram values will also be listed by subject.

Clinically significant abnormalities at screening will be recorded as medical history. Clinically significant abnormalities or worsening of ECG findings observed after the first dose of study drug should be reported as adverse events.

Electrocardiogram results will be listed for each visit, including whether ECG was performed (yes/no), explanation (if not performed), assessment date/time, study date, overall interpretation, and relevant medical history identifier or adverse event identifier if deemed a clinically significant abnormality.

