Record dose of ESA and IV iron	X		Record on an ongoing basis						X		
Record number of missed dialysis visits and reason(s)			Record on an ongoing basis								
IV administration of study drug			Record on an ongoing basis								
Inflammatory biomarker samples ^o			X						X		
Adverse event monitoring	X	X	Record on an ongoing basis						X	X	
Concomitant medications (including antipruritic medications) ^p			X	Record on an ongoing basis						X	X
Structured Safety Evaluation ^f		X		X			X			X	

DP = Discontinuation Period; ESA = erythropoiesis-stimulating agent; F = Friday; IV = intravenous; M = Monday; NRS = numerical rating scale; OOWS = Objective Opiate Withdrawal Scale; PRO = patient-reported outcome; Sa = Saturday; ShOWS = Short Opiate Withdrawal Scale; Th = Thursday; Tu = Tuesday; W = Wednesday

-
- a. Each visit during the Double-blind Treatment Period will coincide with the patient's normal dialysis treatments.
 - b. The End-of-Treatment Visit in the Double-blind Phase will be the first dialysis visit following the last dose of study drug (ie, first dialysis on Week 13 [Day 85]), which also corresponds to Day 1 of the Discontinuation Period (DP Day 1).
 - c. Medical history will be updated on Day 1 with any changes since the Screening Visit, and inclusion/exclusion criteria will be confirmed prior to randomization. Antipruritic medication will be updated at each dialysis visit during the Run-in Period.
 - d. Electrocardiogram must be performed prior to the start of dialysis at screening, Day 85 (End of Treatment), or at Early Termination visit.
 - e. Pre-dialysis vital signs, including body temperature, heart rate, and blood pressure, will be recorded on Days 1, 15, 29, 43, 57, 71 and 85 (End of Treatment), or at Early Termination visit only when the patient is in a sitting or semi-recumbent position. Heart rate will be measured at each dialysis; if heart rate is clinically significant and outside the prespecified visits per Schedule of Events, the heart rate will be recorded on the relevant CRF page.
 - f. Pre-dialysis vital signs, including body temperature, heart rate, and blood pressure, will be recorded at each dialysis visit during the Discontinuation Period. Heart rate will be measured at each dialysis.
 - g. Blood samples for clinical laboratory evaluation will be taken at screening, and on Days 1 and 85 (End of Treatment), or at Early Termination visit only.

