8.8.4 Vital Signs and ECGs

Summary tables will include descriptive statistics for baseline and each postbaseline assessment. Descriptive statistics will be calculated on both the actual score and the

change from baseline score. Baseline is defined as the last measurement taken on or prior to the first day of dosing. Note that the Day 1 assessment can be included in the evaluation of baseline if that the assessment is performed prior to dosing.

If 2 or more evaluations occur in the same visit window, the evaluation closest to the target visit day will be selected for inclusion in the analysis. If multiple evaluations are equally close to the target visit day, then the latest evaluation will be selected for inclusion in the analysis.

All vital sign summaries will include the patients in the Double-blind Safety Population who have at least a postbaseline time point (for criteria based on postbaseline assessments) and with both a baseline and at least 1 postbaseline time point (for criteria evaluating changes from baseline). ≥

Clinically notable vital signs will be identified based on the criteria in [Table 6](#). For each vital sign parameter, the number and percentage of patients with at least 1 notable value will be tabulated by week and overall for the Double-blind Phase.

Table 6. Criteria Used to Identify Clinically Notable Vital Sign Abnormalities

Vital Sign Parameter	Value	Change from Baseline ^a
Systolic blood pressure	≥180 mm Hg	Increase or Decrease of ≥40 mm Hg
	≤90 mm Hg	Decrease of ≥60 mm Hg
Diastolic blood pressure	≥100 mm Hg	Increase or Decrease of ≥20 mm Hg
	≤60 mm Hg	Decrease of ≥40 mm Hg
Heart rate	>130 bpm	Increase of ≥30 bpm
	<55 bpm	Decrease of ≥30 bpm

a. Both value and change from baseline criteria must be met to qualify as a clinically notable abnormality.

All vital signs will be listed in by-patient listings, including visit and collection date/time, and will be sorted by patient identifier and date/time of assessment.

Electrocardiogram results include an overall interpretation of ‘normal,’ ‘abnormal but not clinically significant,’ or ‘abnormal and clinically significant.’ These results will be tabulated at each time point.

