12. CHANGES TO THE ANALYSES PLANNED IN THE PROTOCOL

- The protocol defines clinically notable vital signs based on values observed at the visit and on change from baseline. The definition was updated to remove the criteria based on change from baseline since it was deemed not necessary.
- The protocol states that Akaike information criterion will be used to select the appropriate covariance matrix structure for the MMRM analysis. The SAP uses an unstructured covariance matrix structure as the first choice. Should the model fail to converge, a compound symmetric covariance matrix will be used instead.
- Throughout the protocol, MMRM analyses state that random subject effects will be used, but also provide R-side matrix structures, rendering the random effect (GZ matrix) unnecessary. Random effects have therefore been removed throughout.
- The protocol states that the ShOWS scores on Discontinuation Period Days 1, 2, and 3 and days after Day 3 will be compared between treatment groups using an ANCOVA model. Because scores taken on Day 1 of this period will be included in the model as the subject's baseline score, this analysis was revised to compare ShOWS scores on Discontinuation Period Days 2, 3, and 4, 5, 6 and average assessment on days after Day 6. Additionally, the MMRM analysis was dropped, a categorical analysis was added for OOWS, and text clarifying the OOWS collection times was added.
- The protocol states that adverse events and vital signs potentially related to withdrawal that occur during the 2-week Discontinuation Period will be compared to the adverse events and vital signs reported during the 2-week period preceding the Discontinuation Period. Per the SAP, no comparison to the 2-week period prior to the Discontinuation Period will be made.
- The rules of mapping the early termination visit and the unscheduled visits into a scheduled visit based on visit windows were clarified in the SAP. The protocol states that if 2 or more evaluations occur in the same visit window, the evaluation closest to the target visit day will be selected for inclusion in the analysis. This was revised to select the non-missing value in the order of scheduled visit, early termination visit, and the unscheduled visits.
- The Double blind Discontinuation and Double blind Discontinuation Safety Populations were added.

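### The notable-vital-signs table in SAP 9.5.1 counts subjects already past a cut-off before dosing, so it cannot separate pre-existing from treatment-emergent values and can dilute a between-arm contrast

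*SAP*

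**What the plan says.** Protocol 8.8.4, Table 6, pairs each absolute cut-off with a change from baseline. Its footnote reads: "Both value and change from baseline criteria must be met to qualify as a clinically notable abnormality".

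SAP 9.5.1 says "Clinically notable vital signs will be identified based on the criteria below", and its list holds absolute values only: systolic pressure at or above 180 or at or below 90 mm Hg, diastolic at or above 100 or at or below 60 mm Hg, heart rate above 130 or below 55 bpm. For each parameter "the number and percentage of subjects with at least 1 notable value will be tabulated by week and overall", separately for the Double-blind Treatment Period and the Discontinuation Period. To enter a summary based on post-baseline values, a subject needs only one post-baseline assessment. The section does not exclude subjects notable at baseline, show them in their own column, or plan a shift table.

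SAP 12 declares the change and gives its whole reason: "The definition was updated to remove the criteria based on change from baseline since it was deemed not necessary". SAP 1 gives the SAP primacy over the protocol.

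Other outputs in SAP 9.5.1 do refer to baseline or show the raw data: "Descriptive statistics will be calculated on both the actual values and the change from baseline", and "All vital signs will be listed in by-subject listings, including visit and collection date/time".

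**The concern.** The protocol synopsis names vital signs among the safety endpoints. A reader of a notable-values table wants to know how many subjects became notable on treatment in each arm. The SAP table answers a different question: how many were notable at any time after baseline, whatever their starting point.

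Three features of the plan make this matter.

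- The eligibility criteria (protocol 6.2.1 and 6.2.2) set no numeric limit on blood pressure or heart rate, so subjects already past a cut-off can be randomized. Protocol 6.5.4.4 itself asks that changes be judged against what is usual for the patient.
- The SAP uses a baseline or onset reference elsewhere. Adverse event tables are limited to treatment-emergent events (SAP 9.2), and laboratory tests get a shift summary against the baseline class (SAP 9.4).
- The Discontinuation Period has the same gap. SAP 12 also drops the protocol's comparison of withdrawal-related vital signs with the preceding two weeks, so a second within-subject reference is lost.

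At stake is whether the table can show what arose on treatment, and whether a true difference between arms looks smaller than it is.

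**Working it through.** The plan states no figure for notable vital signs, so there is none to reproduce. The check has two parts: the definitions, then an illustration of size.

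**Definitions.** Take a subject with systolic pressure past 180 mm Hg before the first dose and at a similar level throughout. Under Table 6 the subject is not counted, because the change condition fails. Under SAP 9.5.1 the subject is counted, in the same cell as one who crossed the cut-off after dosing. Table 6 requires both conditions, so every subject it flags is also flagged by the SAP rule; the SAP rule adds subjects whose values did not change enough.

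**Fixed-background illustration.** Inputs: baseline-notable share p0 and new-onset rate e. Neither is in the documents; both are assumed. All baseline-notable subjects are assumed to be notable again.

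- Tabulated rate = p0 + (1 − p0) × e
- Tabulated difference = (1 − p0) × (e on CR845 − e on placebo)

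With e = 10% on CR845 and 5% on placebo (true ratio 2.0, true difference 5.0 points):

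| p0 | CR845 | Placebo | Ratio | Difference |
|---|---|---|---|---|
| 10% | 0.10 + 0.90 × 0.10 = 19.0% | 0.10 + 0.90 × 0.05 = 14.5% | 1.31 | 4.5 points |
| 20% | 0.20 + 0.80 × 0.10 = 28.0% | 0.20 + 0.80 × 0.05 = 24.0% | 1.17 | 4.0 points |
| 30% | 0.30 + 0.70 × 0.10 = 37.0% | 0.30 + 0.70 × 0.05 = 33.5% | 1.10 | 3.5 points |

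The ratio falls quickly, but 90%, 80% or 70% of the absolute difference remains. With 175 per arm (SAP 2.6), the nominal power of a two-sided 5% comparison would be 20%, 13% or 10% for the SAP table, against 39%, 35% or 32% after excluding baseline-notable subjects.

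**Illustration with visit-to-visit variation.** The model above makes recurrence certain and lets the drug act only on the others. A simulation dropped both assumptions: normally distributed subject levels, one baseline reading and six post-baseline readings per subject. Six follows protocol Table 2: "Pre-dialysis vital signs, including body temperature, heart rate, and blood pressure, will be recorded on Days 1, 15, 29, 43, 57, 71 and 85". (The SAP's schedule footnote omits Day 71, which would leave five.) Means, SDs and drug shifts are assumed.

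| Criterion and assumptions | Notable at baseline | SAP rule, placebo v CR845 | Baseline-notable excluded |
|---|---|---|---|
| Systolic ≥180; mean 145, between- and within-subject SD 20 and 15, shift +8 | 8.0% | 23.4% v 35.8%, ratio 1.53, power 0.73 | 18.5% v 30.9%, ratio 1.67, power 0.74 |
| Diastolic ≤60; mean 75, SDs 11 and 9, shift −4 | 14.5% | 38.5% v 51.1%, ratio 1.33, power 0.66 | 30.7% v 44.1%, ratio 1.44, power 0.67 |

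Power barely moves because baseline-notable subjects still carry information here. From the systolic row, the share of them counted again is (0.234 − 0.92 × 0.185) / 0.080, about 80%, on placebo and (0.358 − 0.92 × 0.309) / 0.080, about 92%, on CR845.

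The mixing remains. Of the placebo subjects counted, (0.234 − 0.92 × 0.185) / 0.234, about 27%, were already past the systolic cut-off at baseline. For diastolic the figure is (0.385 − 0.855 × 0.307) / 0.385, about 32%.

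**The case against.** A reader might infer that the table hides a drug effect. The documents do not support that. Randomization balances the baseline-notable share in expectation, so the difference shrinks but does not vanish or reverse. Change-from-baseline statistics at each assessment and full listings remain. Tachycardia, palpitation, syncope and dizziness are adverse events of special interest with their own treatment-emergent tables (SAP 9.2 and 16.3). No safety testing is planned (protocol 8.8), so no test result turns on this table. All of this stands. It leaves a narrower gap: mean changes can miss a few large individual shifts, minimum and maximum show extremes rather than counts, and listings leave the reader to derive the count.

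A reader might also infer an undeclared deviation, or that Table 6 should simply be restored. Neither follows. The change is declared in SAP 12. The value-only rule is the more inclusive one, and Table 6 is not clearly more sensitive: in the systolic simulation, value plus a rise of at least 40 mm Hg gave 4.6% v 11.2%, a larger ratio (2.46) but lower power (0.64).

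Nor do the documents say how often subjects in this population are notable at baseline, or that nearly all of them would recur. Prevalence need not be alike across six cut-offs. Finally, the contrast with laboratory data is only partial: SAP 9.4 also summarizes clinically important values with no stated baseline exclusion. The laboratory shift summary still has no counterpart for vital signs.

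Replacing the SAP table would have its own cost, since it would take already-notable subjects out of the main display. That is a reason to add to the table and not to replace it.

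**Conclusion.** The point holds as one of interpretability. From the text alone, the SAP table cannot separate values that pre-dated treatment from values that arose on it, and the only reason given for removing the baseline reference is that it was not needed.

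It can also dilute a contrast between arms, by an amount the documents do not let anyone fix. With full recurrence, and new onset of 10% v 5%, a ratio of 2.0 shows as 1.31 to 1.10 and a 5.0-point difference as 4.5 to 3.5 points, over an assumed baseline prevalence of 10% to 30%. With ordinary visit-to-visit variation the ratio is lowered more modestly and the loss of power is negligible (0.73 v 0.74 and 0.66 v 0.67). A marked loss of power appears only if baseline-notable subjects recur almost regardless of treatment.

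This is a cheap improvement to a descriptive safety display and does not threaten the trial's conclusions.

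**What to change.** Keep the table in SAP 9.5.1 and add two displays by arm, for each period:

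1. A treatment-emergent count for each criterion: subjects with at least one value past the cut-off whose baseline did not meet the same criterion. The denominator is subjects not notable on that criterion at baseline who have at least one post-baseline value.
2. A shift table of baseline class against worst post-baseline class, with high and low extremes shown separately, so that already-notable subjects stay visible.

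State the baseline for each period: the last value before the first dose for the Treatment Period, and the Day 85 (end-of-treatment) value for the Discontinuation Period. The latter matches the Day 85 baseline that SAP 3 sets for the opiate withdrawal scales. Record the addition in SAP 12.

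The cost is two extra descriptive tables and one derived flag, all from data already collected. Worsening within an already-notable class will still have to be read from the change-from-baseline statistics and listings.
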